## 9 STUDY POPULATION

### 9.1 STUDY POPULATION DEFINITIONS

Community engaged research and implementation designs require multiple levels of participation in a range of study activities (see Figure 1). Study population definitions are summarized below in Table 4.

*Table 4. Study Population Definitions and Nature of Participation*

Population	Definition	Nature of Participation (e.g. Study Activity, Aim)
Community Stakeholders	
Individuals from local communities whose participation is limited to sharing views and opinions of barriers/facilitators to interventions, study approaches
 
INCLUDE:
 
Community Members: Individuals from populations who experience health disparities (PEHD) who have experiences dealing with pain themselves or helping others in pain who are from PEHD (e.g., caregivers, clinicians, etc.)
 
Community Facilitators: Individuals who currently facilitate or could facilitate similar intervention programs as to what is being examined in the project
 
Community Partner Organization Leadership: Individuals in leadership positions at Community Partner Organizations (YMCA of the North, YWCA St. Paul, Hue-MAN Partnership)
	
R61 Quality Improvement Activities (Aims 1-3)
 
R33 Quality Improvement Activities (Aim 3)

Study Participants	Individuals with back pain from populations who experience health disparities (BP-PEHD) and meet inclusion criteria for Randomized Pilot Study (R61) or future Randomized Hybrid Effectiveness-Implementation Trial	
R61 Randomized Pilot Study (Aim 3)
 
R33 Randomized Hybrid Effectiveness Trial (Aims 1-3)

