### 9.2 INCLUSION CRITERIA

The following inclusion criteria apply to the R61 Randomized Pilot Study and the R33 Randomized Hybrid Effectiveness-Implementation Trial.

1. Provide a signed and dated informed consent form
2. State willingness to comply with all study procedures outlined in the consent form
3. Be 18 years of age or older
4. Have self-reported chronic back pain (defined as pain in the low or mid back, or neck pain) which has lasted for 3 months or longer
5. Have a score of 3 or higher on the self-reported Pain, Enjoyment of Life and General Activity (PEG) scale (0 to 10)
6. Be a member of one or more of the following NIH-designated health disparity populations:\*
  - a. American Indian/Alaska Native
  - b. Asian
  - c. Black/African American
  - d. Hispanic/Latino
  - e. Native Hawaiian/Pacific Islanders
  - f. Socioeconomically disadvantaged (annual household income less than \$50,000)

\*This project focuses on back pain in populations that experience health disparities (BP-PEHD). These populations are underrepresented in research studies, have less access to resources for the management of back pain, and have poorer outcomes (see Section 5, Introduction). The study is offered in English, but supplementary materials are available in Spanish for individuals where English is a second language. Supplementary materials may also be offered in other languages.

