### 9.3 EXCLUSION CRITERIA

The following exclusion criteria apply to the R61 Randomized Pilot Study and the R33 Randomized Hybrid Effectiveness-Implementation Trial.

1. Hospitalization for severe mental illness in past six months because the mindfulness and behavioral mind-body practices (e.g., meditation, progressive muscle relaxation, etc.) in the experimental intervention may aggravate symptoms of severe mental illness
2. Active psychotic symptoms, suicidal ideation, or manic episodes in the past three months for the same reasons noted in #1
3. Self-reported cancer with active treatment involving radiation or chemotherapy due to the potential for complications of their back or neck pain and impact on health outcomes
4. Dementia – Mini Mental State Exam score of 23 or lower for those with suspicion of cognitive impairment due to safety risks (e.g., not being able to follow directions for safe physical exercise)
5. Self-reported pregnancy due to the fact that back pain is often associated with pregnancy and differs from non-pregnancy related back pain and thus might have different impacts on health outcomes
6. Children under the age of 18\*

\*Children under the age of 18 will be excluded from the proposed project consistent with NIH Policy and Guidelines on the Inclusion of Children as Participants in Research Involving Human Subjects (<http://grants.nih.gov/grants/guide/notice-files/not98-024.html>). A separate age-appropriate study for children is preferable for several reasons. Most importantly, the self-management education programs are directed toward adults, with content, activities, and exercises that may not be suitable for children. Further, interventions are provided in group settings with facilitated discussions geared towards

challenges faced by adults with back pain. Adapting both the experimental and control interventions for children would require substantial modification, so much so that a separate study is warranted. In addition, many of the biopsychosocial outcome measures proposed for the project were developed specifically for adult populations and have unknown validity or reliability in younger populations.

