### 9.4.1 RECRUITMENT PROCESS

A range of recruitment strategies will be used to recruit Study Participants; these will be initiated approximately 3-6 months prior to screening activities and will continue until enrollment is complete. These include:

- Dissemination of print and digital recruitment materials via routine communication channels (emails, newsletters, etc.) through our Community Partner Organizations and other Community Members
- Giving study and health related presentations in the community to raise awareness about the study
- Participating in local community events (e.g., health fairs) where dissemination of recruitment materials is encouraged
- Using paid advertising (e.g., digital, print, and radio ads) in local media outlets with reach to PEHD
- Listing study on ResearchMatch, an electronic volunteer recruitment registry
- Distributing print and digital flyers and post-cards on UMN campuses and in the community
- Including information about the study in UMN affiliated newsletters (e.g., The Center for Spirituality & Healing, Office of Public Engagement, the Urban Research and Outreach-Engagement Center (UROC), etc.)
- Posting information about the study on UMN affiliated social media (e.g., The Center for Spirituality & Healing and UROC Facebook and Twitter accounts) and websites (e.g., the School of Nursing, the Center for Spirituality & Healing, as well as a unique study landing page)
- Sharing information about the study with other study investigators who have mechanisms in place to query individuals during the consent process regarding their interest in being contacted about additional studies

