## 10 ENROLLMENT PROCEDURES

### 10.1 NUMBER OF STUDY PARTICIPANTS

A total of 30-60 individuals will be enrolled for the R61 Randomized Pilot Study; 376 will be enrolled for the R33 Randomized Hybrid Effectiveness-Implementation Trial.

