## 11 INTERVENTIONS

### 11.1 INTERVENTION OVERVIEW

Both the experimental (Partners4Pain) and active control (Keys to Wellbeing) interventions will be informed by the work conducted in R61 Aims 1 and 2 and research done previously by the investigators (R33AT009110, NH170001, UH3AT008769, R34AT011209). The Template for Intervention Description and Replication (TIDieR) checklist has been and will continue to be used to guide the description of the study interventions to facilitate future results interpretation, as well as dissemination and replication. Consistent with the RE-AIM and ConNECT frameworks guiding this project, we anticipate the interventions will be further shaped and adapted based on stakeholder feedback to meet the needs of

community stakeholders and those with BP-PEHD, based on information gathered in R61 Aims 1 and 2. Elements common to the experimental and control interventions are detailed in Table 5. The investigators have safely and successfully implemented similar group intervention formats in previous studies. Engagement in sessions has been robust (83-92% across in-person and videoconference delivery formats) and no serious adverse events attributable to the interventions have been recorded (n=>500 participants across studies, R33AT009110, NH170001).

*Table 5. TIDieR Intervention Elements Common to Both Groups*

Intervention Specific Participant Resources	Materials and resources that support specific intervention content (see descriptions for Partners4Pain and Keys to Wellbeing). Includes print and electronic workbooks; access to education and skill training videos via a website for viewing in multiple formats (e.g., cell phone, computer tablet, etc.)
Facilitator Materials	Print and electronic manual with session checklists and safety protocols; Google Slide session presentations with embedded expert-led educational and skill training videos; technology and related peripherals (e.g., headsets) as needed
Facilitator Training	Community Facilitators from our Community Partner Organizations with experience leading group programs; 30 hours of competency-based training by the study investigators and Community Facilitators from previous studies

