## 11.2 EXPERIMENTAL INTERVENTION (PARTNERS4PAIN)

Partners4Pain is informed by the COM-B model for behavioral interventions; it postulates that to achieve desired behavioral outcomes (e.g., engagement in positive self-management behaviors such as increased activity, decreased medication use, etc.), interventions must address an individual's capability, opportunity, and motivational related needs. Application of the COM-B model provides guidance for assessing and addressing needs more specifically (e.g., what knowledge, skills, and resources are needed?) and mapping these to evidence based intervention solutions and formats that are most likely to meet the desired outcomes. Importantly, the COM-B model considers affordability, practicality, effectiveness/cost-effectiveness, acceptability, safety, and equity - all critical considerations for implementation and translation of an intervention over the longer term, particularly for populations experiencing health disparities.

Partners4Pain aims to impact pain and behavioral outcomes by addressing BP-PEHD needs for effective pain self-management behaviors. Content unique to Partners4 Pain includes education, skills training, and support in evidence based CIH strategies, (e.g., pain education; BP specific mobility, strength, and stabilization exercises; mindful movement and meditation; progressive muscle relaxation, guided imagery, etc.) augmented by evidence and theory based behavior change techniques (e.g., action planning, problem solving, graded tasks, social support, etc.) which will be built into the program. An important feature of the program will be to provide individuals with resources and support that will empower them to identify what they need (e.g., more information, specific exercises, more or less support from others, etc.) and how to choose which resources are appropriate for them. This approach to self-management is currently being used by the investigators in ongoing studies (R33AT009110, NH170001, UH3AT008769, R34AT011209).

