#### 14.1.1 VIEWS AND OPINIONS

Community Stakeholder and Study Participant views and opinions will be gathered and used to incorporate non-researcher views into the research process, and contribute to co-learning and co-development, which are important features of community engaged research. Data collection methods will include survey questions (closed- and open-ended), interviews, focus groups, field notes; secondary analyses of previous IRB approved qualitative data will also be used.

The schedule of data collection of Community Stakeholder and Study Participant views and opinions can be found in Table 9. This information will augment the investigators previous and ongoing research and the scientific literature.

*Table 9. Schedule of Quality Improvement Data Collection*

Project Population Level	R61 Phase		R33 Phase	Entire Project
Project Population Level	Assess Needs; Optimize Interventions, Approaches (Pre-Pilot Study, Mixed Methods Quality Improvement Activities)	Evaluate Feasibility, Areas for Refinement (Randomized Pilot Study)	Evaluate Effectiveness and Impact of Health Disparities; Assess and Describe Implementation, Disparity Mitigating Factors (Randomized Hybrid Effectiveness-Implementation Trial)	Throughout Project, Time Independent (As they arise)
Community Stakeholders				
Views, opinions re: barriers and facilitators to pain management, self-management identification of capability, opportunity and motivational (COM, BPS), implementation (RE-AIM), and disparity mitigating needs (RE-AIM, ConNECT, COM-APEASE)	X			X
Views, opinions re: solutions to address needs identified above	X			X
Reactions, opinions re: resources and approaches for R61 Pilot Study (e.g., recruitment materials, workbooks, videos, etc.)	X			X
Views and opinions of R61 Pilot Study Results; ideas for optimizing interventions and study approaches for R33 Randomized Trial		X		X
Views and opinions of R33 Randomized Trial Results; ideas for addressing implementation and disparity mitigating needs to prepare for translation to community settings			X	X
Views/opinions re: intervention affordability, practicality, effectiveness, acceptability, safety, and equity; factors that will facilitate adoption, implementation, maintenance (RE-AIM, ConNECT) at community and organizational level			X	X
Study Participants				
Views/opinions re: barriers/facilitators to recruitment, enrollment; reach (RE-AIM)		X	X	

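### R33 eligibility does not exclude people already randomised in the R61 pilot, so some R33 participants may already have had Partners4Pain and the treatment contrast shrinks

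*Combined protocol and SAP*

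**What the plan says.** Section 9.2 opens with "The following inclusion criteria apply to the R61 Randomized Pilot Study and the R33 Randomized Hybrid Effectiveness-Implementation Trial", and Section 9.3 with "The following exclusion criteria apply to the R61 Randomized Pilot Study and the R33 Randomized Hybrid Effectiveness-Implementation Trial". The six exclusions concern recent hospitalisation for severe mental illness; psychosis, suicidal ideation or mania; active cancer treatment; dementia; pregnancy; and age under 18. None refers to earlier participation in this project.

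No other section fills the gap:

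- The examples given for the initial screen (13.2.1) are age, race/ethnicity, pain history and pregnancy.
- Baseline two (13.2.3) re-checks only exclusions that may have arisen since baseline one.
- Randomisation (10.3) is stratified by session offering only.
- Table 6 records use of CIH self-management at baseline one, but not earlier participation in a programme.
- The primary model (15.4.2) has treatment and baseline PEG as its only fixed effects.

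On size, Section 10.1 states: "A total of 30-60 individuals will be enrolled for the R61 Randomized Pilot Study; 376 will be enrolled for the R33" trial. The synopses in 4.1 name the same two partner organisations for both phases, and one recruitment plan (9.4) serves both.

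**The concern.** The pilot trains people in the programme that R33 will test, and R33 then recruits through the same channels under the same criteria. Chronic pain often persists, so a pilot graduate can still meet the PEG threshold, and screening staff have no criterion for declining that person. R33 also offers up to $370 (9.4.4).

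Partners4Pain teaches skills and leaves participants with workbooks and videos. A trained person assigned to Keys already has the content that is meant to separate the arms. A trained person assigned to Partners4Pain probably has less left to gain, and any earlier benefit is already in the baseline PEG. In both cases that person contributes less than a naive participant to the between-group difference. Randomisation balances such people across arms but does not restore the contrast.

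**Working it through.** **Inputs from Section 15.2.2:** difference 0.9 PEG units; SD 2.5 (the stated 0.36 equals 0.9/2.5, which supports 2.5 as the total SD); within-person correlation 0.25; intra-class correlation 0.05; 300 evaluable participants; class size m from 10 to 16; three follow-ups; 20% loss. **Assumed:** 1:1 allocation and two-sided alpha of 0.05, since that section states no alpha.

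**Step 1: reproduce the plan.** Enrolment: 300/0.80 = 375, against 376 stated. For power, I used a normal approximation for the mean of three follow-ups, adjusted for baseline:

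SE = sqrt(2 × [(i + r/3 − i²/(i + r)) + c·m] / 150)

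- Class variance c = 0.05 × 6.25 = 0.3125.
- Person variance i = 0.25 × 6.25 − 0.3125 = 1.25.
- Residual variance r = 6.25 − 0.3125 − 1.25 = 4.6875.
- The person-level term is 1.25 + 1.5625 − 0.263 = 2.549.
- At m = 10, SE = sqrt(2 × 5.674/150) = 0.275. At m = 16, SE = sqrt(2 × 7.549/150) = 0.317.

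Power at 0.9 is 0.905, 0.874, 0.842 and 0.810 for m = 10, 12, 14 and 16. The plan's claim of more than 80% is reproduced.

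**Step 2: the share that the pilot could supply.** With 1:1 allocation, a pilot of 30 to 60 trains 15 to 30 people in Partners4Pain. The shares of 376 are:

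- 30/376 = 8.0%: every trainee of a 60-person pilot re-enrols.
- 15/376 = 4.0%: half of those 30, or every trainee of a 30-person pilot.
- 7.5/376 = 2.0%: a quarter of the 30.

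**Step 3: dilution.** If a share f adds nothing to the contrast (full carry-over), the difference is 0.9 × (1 − f).

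| f | Difference | Power, m = 10 | Power, m = 16 |
|---|---|---|---|
| 0 | 0.900 | 0.905 | 0.810 |
| 2% | 0.882 | 0.894 | 0.794 |
| 4% | 0.864 | 0.881 | 0.777 |
| 8% | 0.828 | 0.853 | 0.742 |

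With half carry-over the loss in the difference is halved: at 8%, 0.9 × (1 − 0.04) = 0.864. Power falls below 80% at f of about 14% (m = 10), 10% (m = 12), 5% (m = 14) and 1% (m = 16). The low figure at m = 16 arises because power there is only 0.81 before any dilution.

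**The case against.** The 8% figure stacks several ceilings: the largest pilot, every trainee still at PEG 3 or above, every one re-enrolling, and no contrast left in any of them. The last is doubtful, since people whose pain persists after one course might still gain from a second. The lowest power figures also need every class at 16, while Table 5 allows 7 to 16. Section 15.2.2 first states its target as about one unit, and 1.0 × 0.92 = 0.92 is still above 0.9. That shows some margin, although the same section also calls 0.9 clinically meaningful. Finally, this is an effectiveness trial that leaves outside exercise and complementary care unrestricted (11.6). All of this bears on size and stands. It does not supply the missing criterion, and training in the test programme itself differs from general background care.

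Two wider readings are tempting, and the documents do not support them:

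- **The team's other trials as a measurable source.** Section 9.4.1 lists "Sharing information about the study with other study investigators who have mechanisms in place to query individuals during the consent process", Section 11.2 says "This approach to self-management is currently being used by the investigators in ongoing studies", and Section 11.1 cites "n=>500 participants across studies, R33AT009110, NH170001". But 9.4.1 names no related trial, and the 500 are not broken down by arm, pain status or health-disparity membership. No share of R33 can be derived from them.
- **Stakeholder reviewers as pre-trained.** Table 4 includes as Community Members "Individuals from populations who experience health disparities (PEHD) who have experiences dealing with pain themselves", and Table 9 has stakeholders giving "Reactions, opinions re: resources and approaches for R61 Pilot Study (e.g., recruitment materials, workbooks, videos, etc". Table 4 confines that role to sharing views. This is not an exclusion, so they could enrol later, but commenting on materials is brief exposure and not nine sessions of training.

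Barring everyone from either group would be too broad. It would remove people who only ever had Keys, and community members whose feedback the project asked for.

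**Conclusion.** The gap is real: Sections 9.2 and 9.3 let an R61 Partners4Pain graduate into R33, and nothing in screening, stratification or the primary model bars, records or adjusts for it. The consequence is a modest loss of contrast and power. A reader might infer a bias that favours one arm, but the documents do not support that, because randomisation distributes earlier trainees over both arms.

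From the pilot alone the planning difference falls from 0.9 to no less than about 0.83, which costs about 5 to 7 points of power. At the smaller shares of 2% to 4% it falls to about 0.88 to 0.86, which costs about 1 to 3 points. These figures rest on 1:1 allocation, full carry-over and assumed re-enrolment; the documents give neither re-enrolment nor carry-over. The sample size calculation itself is not in question. The change is worth making because it is cheap and because the margin over 80% is thin when classes are large.

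**What to change.** Add to Section 9.3, for R33 only, the exclusion *previously randomised in the R61 pilot*, and check it at the initial screen against the study's own REDCap enrolment list. Basing it on randomisation, whichever arm was assigned, means that nobody has to look up the pilot allocation.

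Do not exclude people for earlier participation in the team's related self-management trials or for stakeholder review of the materials. Record both with one baseline question, and pre-specify in Section 15.4.2 a sensitivity analysis that refits the primary model without those people. Because the exposure is recorded before randomisation, leaving them out does not break the randomised comparison.

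The cost is one exclusion line, one question, one list check and the loss of a small number of easily reached volunteers (at most the 30 to 60 pilot participants). N stays 376. Section 6.1 requires the R33 protocol to go to NCCIH before the transition request, so the edit can be made then.

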## 9.4 RECRUITMENT & RETENTION

Potential Community Stakeholders for the R61 and R33 Quality Improvement Activities will be identified through the routine communication channels of our Community Partnership Organizations (e.g., system-wide emails, newsletters, organizational meetings, presentations, etc.).

Study Participants (See Section 9.1 Study Population Definitions) for the R61 Randomized Pilot Study and the R33 Randomized Hybrid Effectiveness-Implementation Trial will be identified as described below.

### 9.4.1 RECRUITMENT PROCESS

A range of recruitment strategies will be used to recruit Study Participants; these will be initiated approximately 3-6 months prior to screening activities and will continue until enrollment is complete. These include:

- Dissemination of print and digital recruitment materials via routine communication channels (emails, newsletters, etc.) through our Community Partner Organizations and other Community Members
- Giving study and health related presentations in the community to raise awareness about the study
- Participating in local community events (e.g., health fairs) where dissemination of recruitment materials is encouraged
- Using paid advertising (e.g., digital, print, and radio ads) in local media outlets with reach to PEHD
- Listing study on ResearchMatch, an electronic volunteer recruitment registry
- Distributing print and digital flyers and post-cards on UMN campuses and in the community
- Including information about the study in UMN affiliated newsletters (e.g., The Center for Spirituality & Healing, Office of Public Engagement, the Urban Research and Outreach-Engagement Center (UROC), etc.)
- Posting information about the study on UMN affiliated social media (e.g., The Center for Spirituality & Healing and UROC Facebook and Twitter accounts) and websites (e.g., the School of Nursing, the Center for Spirituality & Healing, as well as a unique study landing page)
- Sharing information about the study with other study investigators who have mechanisms in place to query individuals during the consent process regarding their interest in being contacted about additional studies

